### 9.8.3 Investigational medicinal product accountability

The investigator is fully responsible for the IMPs at the trial site and for maintaining adequate control of the IMPs and for documenting all transactions with them.

Dispensing of IMPs may be delegated, e.g. to a hospital pharmacy, as locally applicable and must be documented in the site signature and designation of responsibility log.

Documentation of IMP accountability must be kept for the IMPs administered to each individual subject randomised in the trial. This documentation must be available during monitoring visits and will be checked by an unblinded CRA to verify correct administration of the IMPs. Drug accountability information will be recorded by unblinded site staff for individual drug accountability per subjects as well as for the inventory status of all IMPs at the trial site on paper forms.

All [unused] IMPs (including packaging material) supplied by the contract manufacturing organisation (CMO) on behalf of LEO Pharma will be returned to the CMO. Prior to their return, the IMP must be fully accounted for by the unblinded CRA with the help of the unblinded site staff. Accountability must be documented on drug accountability forms.

Page 63 of 129

IMPs will be returned from the trial site to the CMO directly. For more information about handling of IMPs at site, including drug accountability and reconciliation, please refer to the Trial Product Handling Manual.

### 9.8.4 Treatment compliance

IMP injections will be performed by unblinded site staff who will document the total number of injections administered per treatment day in the eCRF.

In case of non-compliance, details which injection was not administered in the comparator treatment group (i.e., Dupixent® or saline) will be documented as specified in the blinding plan.

### Reporting in eCRF

The following data will be recorded in the eCRF:

- IMP application according to dosing schedule (yes, no); If no, a reason will be given.
- Primary reason for non-compliance lack of time, adverse event, other (if other, a specification should be provided).
- Date and time of injections (stated for each of the injections per visit separately).
- Site of injection: For the site (upper leg [thigh], stomach area [abdomen] or in the upper, outer arm) the laterality should be specified (right or left).

### 9.8.5 Trial product destruction

All used LEO 138559 vials and unused IMP must be returned to the CMO and will be destroyed by the CMO according to approved procedures and/or local requirements.

Empty comparator syringes and syringes used for administration of IMP and saline solution can be destroyed at site provided the trial site has procedures in place for such destruction.

Trial sites which do not have such IMP destruction procedures in place will dispose used IMP syringes in sharps bins which will be shipped to the CMO.

### 9.9 Provision for subject care following trial completion

In order to ensure appropriate treatment of the subjects after they have completed the trial, the subjects will be treated at the investigator's discretion or referred to other physician(s) according to standard practice.

### 9.10 Reporting product complaints

Any defects or issues with the IMP must be reported to the Quality department via Global Safety at LEO Pharma on the trial-specific (paper) complaint form within 3 days of first knowledge.

Critical complaints (defined as any defect, issue, that has or potentially could have a serious impact on the subject [e.g. SAE or large particles in the vial) must be reported to the Quality department via Global Safety within 24 hours of knowledge.

Complaint forms should contain a detailed description of the defect, issue, including whether it led to an AE. (S)AEs which occur due to a defect or issue with the IMP will be reported by the investigator as described in Sections 13.3 and 13.4.

During the investigation of the product complaint, the IMP must be stored at labelled conditions unless otherwise instructed; the trial site will be notified whether the IMP needs to be returned for further investigation or may be destroyed.

Global Safety, LEO Pharma contact information for reporting product complaints:

[contact]

E-mail address: [contact]

### 10 Discontinuation and withdrawal

## 10.1 General principles

A subject may withdraw from the trial (prior to first dose or during the treatment period) or permanently discontinue trial treatment at any time if the subject, the investigator, or LEO Pharma considers that it is not in the subject's best interest to continue.

A subject who withdraws from the trial is a subject who stops treatment with the IMP and all further protocol defined trial activities. A subject who permanently discontinues IMP is a subject who, although they stop treatment with the IMP, agree to their follow-up as described in Section 10.3. Early termination assessments to be conducted for both events are described in Section 10.3.

If a subject withdraws from the trial, they may request destruction of any samples taken and not tested. The investigator must document this in the subject's medical record and inform LEO Pharma.

#### 10.2 Reasons for discontinuation of IMP

### 10.2.1 Reasons for permanent discontinuation of IMP

Subjects will permanently discontinue IMP in the event of:

- Withdrawal by subject
- An AE that, in the opinion of the investigator or sponsor's medical expert, contraindicates further dosing.
- Confirmed clinically significantly abnormal ECG or change in ECG.
- Initiation of prohibited medication which cannot be safely replaced by other non-prohibited medications.
- Evidence of pregnancy, or if the subject is noncompliant with the contraception requirements (see Section 8.2).
- Symptomatic infection with SARS-CoV-2 that is likely to have an impact on efficacy or safety data (i.e., patients with a SARS-CoV-2 infection without or very mild symptoms only (e.g., rhinitis or sore throat) might continue with the study at investigator's discretion and in accordance with the applicable local regulations)..
- Other reasons, at the discretion of the investigator. If other, a specification should be provided.

Page 66 of 129

It is not allowed to restart IMP treatment after discontinuation of IMP.

#### Data to be recorded in the eCRF

The date and time of last dose for IMP will be recorded in the eCRF. The primary reason for permanent discontinuation of IMP must be recorded in the medical records and on the end-of-treatment form in the eCRF where the following options are available:

- Death.
- Pregnancy.
- Adverse event.
- Use of prohibited concomitant medication
- Lack of efficacy.
- Withdrawal by subject.
- Lost to follow-up.
- Other.

If 'adverse event' or 'other' is selected, a specification must be provided in the eCRF. If adverse event is selected, the AE in question will be linked to the IMP discontinuation.

If 'withdrawal by subject' is selected, it will be recorded whether the subject withdrew informed consent or not.

Discontinuation of IMP due to COVID-19 pandemic will be collected and specified in the 'Other' category.

### 10.2.2 Reasons for temporary discontinuation of IMP

IMP dosing may be temporarily suspended in the event of:

• COVID-19 related disruption leading to site closure.

A decision to discontinue IMP temporarily or to reinstitute IMP treatment must be discussed with sponsor's medical expert. However, the investigator may suspend trial treatment at any time, even without consultation with sponsor's medical expert if the urgency of the situation requires immediate action and if this is determined to be in the subject's best interest. In such cases, sponsor's medical expert should be informed as soon as possible.

### 10.3 Early termination assessments

#### Permanent discontinuation of IMP

Subjects who permanently discontinue IMP for any reason will be asked to attend an early termination visit as soon as possible after last administration of IMP and return to the trial site for additional visits as indicated below:

- An early IMP termination visit as soon as possible after last dose of IMP (in case of early termination before week 4: a nominal week 4 visit)
- An end of trial visit (safety follow-up visit 16 weeks after last administration of IMP).

See the schedule of trial procedures (Section 4) for data to be collected at these visits. The subjects will be asked to complete the diary until end of trial visit. The investigator will review any AEs which will be followed up according to Section 13.7, if the subject agrees.

Details on data to be recorded in the eCRF for subjects who permanently discontinue IMP can be found in Section 11.8.

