End-of-trial form														X	X		

- a) Screening will be performed up to 4 weeks before the baseline visit. If the screening visit is performed close to the beginning of the washout period, no additional washout phone call is necessary, at the discretion of the investigator.
- b) Subjects who permanently discontinue IMP treatment prior to week 4 will be asked to return to the trial site for a primary endpoint (nominal week 4) visit.
- c) An end-of-treatment form must be completed in the eCRF for all randomised subjects.
- d) An end-of-trial form must be completed in the eCRF for all randomised subjects.
- e) Subjects who permanently discontinue IMP prior to week 16 and subjects who withdraw from the trial will be asked to come to an early termination visit. As an early termination visit will only be performed in case of subjects permanently discontinuing the IMP, the visit has been marked with an (X).
- f) Unscheduled visit(s) between planned visits may be added to the subject's visit schedule if judged necessary by the investigator, e.g. due to an AE, a significant change in disease state, or difficulty complying with the clinical trial protocol requirements. At an unscheduled visit, the investigator should at least collect AEs

Version: 5.0

- data. Other assessments/procedures to be conducted at an unscheduled visit will be at the discretion of the investigator. As unscheduled visits will only be performed if judged necessary by the investigator, the assessments/procedures have been marked with an (X).
- g) The informed consent form must be signed prior to performing any protocol-related procedures, including but not limited to screening evaluations and washout of disallowed medications.
- h) In case medical history is incomplete at the screening visit because prior and concomitant diseases were not communicated by patient before or e.g. in case of abnormal lab values from screening assessments, missing data will be documented at week 0 (baseline).
- i) Mycobacterium tuberculosis IFN-γ release assay (or a PPD test if it is a requirement from the local health authorities).
- j) For women of childbearing potential
- k) Preparation, administration and handling of IMPs will only be performed by unblinded site staff
- l) All subjects must use an emollient twice daily (or more frequently, if needed) for at least 7 days before day 1 (baseline) and throughout the treatment period (until week 16).

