#### **Pharmacokinetics**

Based on the human PK data from the FiH trial, the PK of LEO 138559 is as expected for a mAb (IgG1) directed toward a membrane-bound target, and the target-mediated drug disposition (TMDD) characteristics are also visible in the observed human data as it was in the cynomolgus data.

After SC administration, LEO 138559 is slowly absorbed with a mean time to maximum concentration of approximately 7.5 days. After multiple dosing, the elimination half-life was observed to be between 21–25 days. At and above the exposure level relevant for clinical testing (150 mg Q2W), the elimination is dominated by linear clearance and close to dose-proportionality is expected at steady state. The exposure at steady state following administration of 450 mg Q2W is expected to result in lower exposure than 450 mg every week for 5 weeks (the highest dose in the LP0145-1315 trial).

A detailed overview of clinical data on LEO 138559 is available in the current investigator's brochure [36].

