#### Safety follow-up period (week 17 to week 32)

In the safety follow-up period, the subject will not receive any treatment with LEO 138559 or comparator injections. The safety of the subject will further be assessed at 3 safety follow-up phone calls (weeks 20, 24, and 28) and at a final safety follow-up visit at week 32. Topical treatment for AD will be permissible during the safety follow-up period. At the end of trial visit the diary will be collected and assessments will be conducted as specified in Panel 2.

Subjects who require treatment with other biologics will prematurely discontinue the trial.

Subjects who discontinue the trial early should be requested to return for an early termination / end of trial visit (see also Section 10.3) at the time of the decision to withdraw from the study.

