# 13.2 Collection of adverse event reports

AE data must be collected from time of first trial-related activity after the subject has signed the informed consent form (ICF) until subject's completion of the clinical trial (safety follow-up visit at week 32 see Section 7.3)

AEs must be assessed by a physician.

At all visits, the subject will be asked a non-leading question by the investigator about AEs, e.g.: "How have you felt since I saw you last?" No specific symptoms should be asked for. It is important that the investigator also observes the subject for any changes not reported by the subject and records these changes.

Principles for data entry in the eCRF are described in Sections 11.4.1 to 11.4.5

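### Subjects who stop IMP early but stay in the trial can have 12 to 14 weeks without a scheduled safety contact, because the three safety calls are fixed to trial weeks and not to last dose

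*Combined protocol and SAP*

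**What the plan says.** Protocol Section 10.3 (Permanent discontinuation of IMP) lists two contacts for subjects who stop IMP and agree to follow-up. The first is given as "An early IMP termination visit as soon as possible after last dose of IMP (in case of early termination before week 4: a nominal week"; the bracket refers to the week 4 visit. The second is "An end of trial visit (safety follow-up visit 16 weeks after last administration of IMP"). It adds that AEs are reviewed and followed up under Section 13.7 if the subject agrees, and that the diary continues to the end-of-trial visit.

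The calls are defined in Section 7.1 (Safety follow-up period): "3 safety follow-up phone calls (weeks 20, 24, and 28"). Panel 2 gives them as visits 13 to 15 at the same trial weeks. Neither place ties them to the last dose, and neither says whether a subject who stopped early receives them.

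Two Panel 2 footnotes bear on the first contact. Footnote b reads: "Subjects who permanently discontinue IMP treatment prior to week 4 will be asked to return to the trial site for a primary endpoint (nominal". The visit meant is again the one at week 4. Footnote e reads: "Subjects who permanently discontinue IMP prior to week 16 and subjects who withdraw from the trial will be asked to come to an early termination". Together they ask for both visits when IMP stops before week 4. The bracket in 10.3 can be read as one replacing the other.

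New AEs are elicited at contacts. Section 13.2: "At all visits, the subject will be asked a non-leading question by the investigator about AEs". On persistence of drug, Section 5.2 says: "After multiple dosing, the elimination half-life was observed to be between". The range it gives is 21 to 25 days.

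**The concern.** A completer has a scheduled safety contact every four weeks after treatment, at weeks 16, 20, 24, 28 and 32. A subject who stops early has fewer, and if the stop is early enough the three calls fall too late to help. Early stoppers include subjects who stopped because of an AE or an infection, so scheduled follow-up is thinnest where safety information is of most interest.

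Section 5.5 names infection, delayed healing and hypersensitivity as important potential risks of LEO 138559. A new event of this kind in the gap, if the subject did not come forward, would first be asked about at the end-of-trial visit and dated from memory. Onset, severity and treatment would then be recorded less well for these subjects than for completers. Section 14.3.9.1 reports event rates per 100 patient-years of observation time, so weeks in which nobody is scheduled to ask would still count in the denominator. Safety of LEO 138559 is the trial's secondary objective.

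**Working it through.** The plan states no figure for this gap, so there is none to reproduce. The check is calendar arithmetic and an elimination calculation.

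**Inputs**
- End-of-trial visit for discontinuers: last dose week L + 16 (Section 10.3).
- Calls: weeks 20, 24, 28 (Section 7.1, Panel 2). Panel 2 days follow from day = 7 × week + 1: weeks 20, 24, 28, 32 give days 141, 169, 197, 225, which match.
- Dosing visits before the final dose at week 14: weeks 0, 1, 2, 4, 6, 8, 10, 12 (Panel 2).
- Start of gap, t: week 4 if IMP stops before week 4; otherwise the termination visit. Section 10.3 asks for that visit as soon as possible. I take L + 2 and then vary it.
- Half-life of LEO 138559: 21 to 25 days (Section 5.2).

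**Longest scheduled gap in weeks** = the largest step between consecutive points in t, any calls before L + 16, and L + 16.

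| Last dose L | t | End of trial | Calls before it | Gap, calls not applied | Gap, calls applied |
|---|---|---|---|---|---|
| 0 | 4 | 16 | none | 12 | 12 |
| 1 | 4 | 17 | none | 13 | 13 |
| 2 | 4 | 18 | none | 14 | 14 |
| 4 | 6 | 20 | none (week 20 coincides) | 14 | 14 |
| 6 | 8 | 22 | 20 | 14 | 12 |
| 8 | 10 | 24 | 20 | 14 | 10 |
| 10 | 12 | 26 | 20, 24 | 14 | 8 |
| 12 | 14 | 28 | 20, 24 | 14 | 6 |

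Completers: 20 − 16 = 24 − 20 = 28 − 24 = 32 − 28 = 4 weeks.

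**Sensitivity to the termination visit.** If it follows the last dose at once (t = L), the gap for L = 4 to 12 approaches 16 weeks without the calls. With the calls it is 16, 14, 12, 10 and 8 weeks for L = 4, 6, 8, 10 and 12.

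**Elimination over the gap**, fraction = 1 − 0.5^(days / half-life), mono-exponential:
- 14 weeks = 98 days: 98/21 = 4.67 half-lives, 96%; 98/25 = 3.92 half-lives, 93%.
- 12 weeks = 84 days: 84/21 = 4.00, 94%; 84/25 = 3.36, 90%.

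**Remaining from the last dose**, 0.5^(days / half-life):
- Day 14: 63% to 68%.
- Day 112 (16 weeks): 2.5% to 4.5%.
- Counting decay from the mean time to maximum concentration of about 7.5 days (Section 5.2) gives 81% to 84% and 3% to 6%. The picture is the same.

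**The case against.** The strongest reply is that a gap in scheduled contact is not a loss of contact. A reader might infer that subjects stopped for an AE go unseen for 14 weeks, or that nothing in the plan would pick up a new event. The documents do not support either reading:
- Section 10.3 sends AEs to follow-up under Section 13.7, which asks the investigator to follow all AEs to outcome during the trial.
- Section 7.1 allows an unscheduled visit at any time, and Panel 2 footnote f requires AE collection there.
- The subject card (Appendix 3B) carries site and investigator numbers.
- The diary (Section 11.7.1.1) records other medication, so a treated event may leave a dated trace.

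All of that stands, but it has limits. Section 13.7 concerns AEs already known, sets no contact interval, and for these subjects depends on their agreement. Unscheduled visits and the card need someone to raise the problem first. The diary covers itch, emollients and medication, not AEs.

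A reader might also take 14 weeks as the general figure. It is not: if the fixed calls apply, later stops have shorter gaps. Nor should subjects stopped for a confirmed ECG abnormality be counted here. Section 11.4.4 withdraws them from the trial, so the withdrawal part of Section 10.3 governs.

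Last, the effect on the analysis is limited. The secondary endpoint counts treatment-emergent AEs to week 16 (Section 14.3.6), and L + 16 is never before week 16, so an attended end-of-trial visit covers that window. What suffers is quality of recall, in a 12-subject descriptive trial.

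**Conclusion.** The point holds for scheduled contact with subjects who stop IMP and remain in the trial. For a last dose at week 4 or earlier, the calls give no earlier contact whether or not they apply to discontinuers. The scheduled gap is 12 to 14 weeks, against 4 weeks for completers. For L = 4 this takes the termination visit at week 6; an immediate visit makes it nearly 16 weeks. For later stops it is 6 to 12 weeks if the calls apply (termination visit two weeks after last dose) and about 14 to nearly 16 weeks if they do not. The plan does not settle which.

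The 93% to 96% elimination figure is for a 14-week gap and assumes linear elimination. Section 5.2 also describes target-mediated disposition, and the documents give no half-life for dupilumab, so the figure covers LEO 138559 only. One such subject would be 1/8 = 12.5% of the planned LEO 138559 arm, but the documents give no expected discontinuation rate.

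This is a worthwhile, inexpensive improvement to AE ascertainment. It does not show that subjects are unprotected. A related mismatch should be settled at the same time: Section 14.3.6 sets the treatment-emergent limit at 18 weeks after last dose, which matches completers (32 − 14 = 18), while discontinuers' last visit is at 16 weeks.

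**What to change.** Reconcile Section 10.3, Section 7.1 and Panel 2 (footnotes b and e):
1. State that visits 13 to 15 apply to subjects who stop IMP early and remain in the trial.
2. For these subjects, time the calls from the termination visit (or the nominal week 4 visit that takes its place) at the protocol's own 4-week spacing, up to the end-of-trial visit. Content stays as in Panel 2: AEs, concomitant medication, diary check.
3. State whether a stop before week 4 leads to one visit or two.

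Examples: last dose week 2 gives calls at weeks 8, 12 and 16 and end of trial at week 18. Last dose week 4 with termination at week 6 gives calls at weeks 10, 14 and 18 and end of trial at week 20. The longest scheduled gap is then 4 weeks, as for completers.

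Cost: up to three phone calls per early discontinuer and a short amendment, with no new procedure or staff. For a last dose at week 4 or earlier, the calls take the place of ones that would fall at or after the end-of-trial visit. For later stops, one or two fixed calls already precede that visit if the calls are taken to apply, so part of the effort is already planned.

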#### Withdrawal from trial

Subjects who withdraw from the trial after first dose of IMP for any reason will be asked to attend an early termination visit as soon as possible after last administration of IMP (see the schedule of trial procedures [Section 4] for data to be collected at an early termination visit). The investigator will review any AEs which will be followed up according to Section 13.7, if the subject agrees.

Details on data to be recorded in the eCRF for subjects who withdraw from the trial can be found in Section 11.8.

## 10.4 Lost to follow-up

A subject will be considered lost to follow-up if they repeatedly fail to return for scheduled visits and if the trial site is not able to get in contact with the subject.

The following actions must be taken if a subject fails to return to the trial site for a required visit:

• The trial site must attempt to contact the subject and reschedule the missed visit as soon as possible and counsel the subject on the importance of maintaining the assigned visit schedule and ascertain whether the subject wishes to continue in the trial.

Page 68 of 129

Before a subject is deemed lost to follow-up, the investigator or designee must make every
effort to regain contact with the subject. These contact attempts should be documented in
the subject's medical record. Should the subject continue to be unreachable, they will be
considered to have withdrawn from the trial with a primary reason of lost to follow-up.

[figure not shown]
Version: 5.0

